4.2.14 Vital signs

All vital signs variables including height, weight and BMI will be summarized by absolute value at each visit by treatment/weight group using the safety analysis set, together with the corresponding changes from baseline. These summaries will be produced for the on-treatment period, as defined in section 3.1.3. The summary statistics presented will be the minimum, 1st quartile, median, 3rd quartile, maximum, mean and SD. The normal reference ranges listed in Table 2 and Table 3 will be used for the identification of individual abnormalities. A shift table will be produced for each vital sign variable to display low, normal, high and missing values. The shift tables will present baseline and maximum/minimum/last post-baseline values for each variable.

Shift plots showing each individual patient's vital signs value at baseline and at maximum/minimum/last value post-baseline will be produced for each continuous vital sign variable.

All recorded vital signs data will be listed.

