4.3 Justification for dose

Clinical asthma manifestations and treatment responses in children (6 to 11 years of age) and adolescents (12 to 17 years of age) are similar to the adult population (Weiss and Ware 1996). For several marketed or emerging therapeutic mAbs (adalimumab, basiliximab, canakinumab, eculizumab, and omalizumab), children typically receive the same fixed dose as for adults if their body weight is greater than 30 to 40 kg or the same weight-based intravenous dose (ie, infliximab and daclizumab) as in adults (Xu et al 2013). For the lower body weight strata, a dose is typically selected to match PK exposure of the adult efficacious dose using, for example, a population PK model.

A population PK model for benralizumab was previously developed with data from 8 clinical studies (SIROCCO, CALIMA, BISE, MI-CP158, MI-CP166, MI-CP186, MI-CP197 and MI-CP220). In this population PK model, weight was identified as a significant covariate. The PK profile for children 6 to 11 years of age weighing <35 kg was simulated using the weight distribution in the CDC growth chart assuming it was equally likely to recruit females and males at any age within the age group. The ^{CCI} mg dose was selected for children aged 6 to 11 years weighing <35 kg as the steady-state PK exposure was projected to be comparable to that of the adult efficacious dose, ^{CCI} mg. Based on the PK/PD relationship, blood eosinophils were predicted to attain near complete depletion.

In the pivotal Phase 3 studies, adult and adolescent (12 to 17 years old) patients were enrolled and randomised to receive placebo, 30 mg every 4 weeks (Q4W), and 30 mg Q8W. In these studies, there was no apparent advantage to more frequent dosing (Q4W). The safety profile in adolescents was consistent with the profile in adults and the more frequent regimen of 30 mg Q4W was well tolerated in both populations. Moreover, no exposure-related increase in TEAEs was observed in adult patients receiving 100 mg Q8W (more than three times the recommended clinical dose for the asthma indication).

Patients aged 12 to 14 years will receive **CC1** mg of benralizumab (MEDI-563) for SC injection during the study, irrespective of their body weight when enrolled, consistent with the approved dose of benralizumab in patients of this age.

The percentage and titre of ADAs and the impact of ADAs on the PK profile were assumed to be the same for children and for adults.

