- 6 A well-documented requirement for regular treatment with ICS: total daily dose equivalent to ≥ 250 μg fluticasone propionate, or ≥ 400 μg budesonide (≥ 320 μg budesonide ex-actuator), or ≥ 200 μg fluticasone furoate, or ≥ 220 μg mometasone furoate, or ≥ 160 μg ciclesonide, or ≥ 1000 μg triamcinolone acetonide, or ≥ 500 μg beclomethasone dipropionate, or ≥ 200 μg beclomethasone dipropionate (HFA) in the 12 months prior to Visit 1, with or without maintenance oral corticosteroids. Medium dose ICS as per local guidelines will also satisfy the inclusion criterion after agreement with the Study Physician.
- 7 Current treatment with at least 1 additional controller medication, such as inhaled LABA, leukotriene receptor antagonist, long acting anti-muscarinic agent, or theophylline, since at least 3 months prior to Visit 1.
- 8 Forced expiratory volume in 1 second (FEV₁): Flow/ volume curve indicating airflow obstruction at either Visit 1 or 2 (performed prior to first dose of study medication), associated with: a pre-bronchodilator FEV₁ $\leq 110\%$ predicted normal, or, FEV₁/Forced Vital Capacity ratio ≤ 0.8 .

Weight

- 9 Body weight ≥ 15 kg.

Sex

- 10 Male or female

Reproduction

- 11 Females of childbearing potential (FOCBP) who are sexually active, as judged by the investigator, must commit to consistent and correct use of an acceptable method of contraception for the duration of the study and for 12 weeks after the last dose of IP.

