3.3.6.3 Vital signs

Vital signs such as systolic blood pressure, diastolic blood pressure, pulse rate, weight, height, Body mass index (BMI) and body temperature will be assessed. The assessment will be conducted while sitting with a completely automated device with a calibrated manometer using an appropriate pediatric cuff and in accordance with the visit schedule provided in Table 1 of the CSP.

Changes in the vital signs variables between baseline and each subsequent scheduled assessment will be calculated. Absolute values will be compared to the given reference ranges ([Table 2](#) and [Table 3](#)) and classified as low (below range), normal (within range or on limits) or high (above range). All values (absolute) falling outside the reference ranges will be flagged in the listings.

Table 2: Vital signs reference ranges for age 6 -11 years

Parameter	Standard Units	Lower Limit	Upper Limit
Diastolic Blood Pressure	mmHg	57	80
Systolic Blood Pressure	mmHg	97	120
Pulse Rate	Beats/min	70	110
Body Temperature	Celsius	35.5	37.5
Weight	kg	15	NA
Height	cm	NA	NA

Table 3: Vital signs reference ranges for age 12 -14 years

Parameter	Standard Units	Lower Limit	Upper Limit
Diastolic Blood Pressure	mmHg	64	83
Systolic Blood Pressure	mmHg	110	131
Pulse Rate	Beats/min	55	105
Body Temperature	Celsius	35.5	37.5
Weight	kg	15	NA
Height	cm	NA	NA

BMI will be calculated from the height and weight as follows:

$$\text{BMI (kg/m}^2\text{)} = \text{weight (kg)} / (\text{height (m)})^2$$

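### The SAP's limits for weight, height and BMI cannot flag slowed growth, and its other outputs would reveal only weight loss or arrested growth

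*SAP*

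**What the plan says.** SAP 3.3.6.3 groups weight, height and BMI with the vital signs, and SAP 4.2.14 sets the scale of the summaries: "All vital signs variables including height, weight and BMI will be summarized by absolute value at each visit". The rule for all of them is "Absolute values will be compared to the given reference ranges", giving low, normal (limits included) or high. SAP 4.2.14 repeats it: "The normal reference ranges listed in Table 2 and Table 3 will be used for the identification of individual abnormalities". The same section requires: "A shift table will be produced for each vital sign variable to display low, normal, high and missing values".

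SAP Tables 2 (ages 6-11) and 3 (ages 12-14) have identical rows for body size: "Weight kg 15 NA" and "Height cm NA NA". Neither table has a BMI row. The blood pressure and pulse limits do differ between the two tables.

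Protocol 5.1, criterion 9, sets the entry minimum: "Body weight ≥ 15 kg". Protocol Table 1 schedules weight and height at screening and Weeks 16, 24 and 48.

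Besides the shift tables, 4.2.14 plans by-visit summaries of value and change (with minimum and quartiles), individual shift plots of baseline against maximum, minimum and last value, and a full listing. Neither document plans a z-score, percentile or growth velocity for outcome data. A growth reference appears only in the dose simulation in Protocol 4.3, "using the weight distribution in the CDC growth chart".

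**The concern.** Long-term safety in children is in the study title, and Part B exists to evaluate safety. A reader of the study report would expect the body-size tables to say whether children kept growing as they should.

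The shift tables cannot say so. Every eligible child starts as normal for weight, and failure to gain never changes that class. Height and BMI cannot be classed low or high at all.

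The summaries of absolute value and change have a different weakness. In growing children a positive mean change is expected, and with no control arm nothing in the output says how large it should be. Partly slowed growth would appear as a gain.

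**Working it through.** **1. The weight floor.** The lower limit is 15 kg (SAP Tables 2 and 3) and the entry minimum is 15 kg (Protocol 5.1). A value on the limit counts as normal, so no eligible child can be low at baseline. The loss needed to reach the limit is (w - 15)/w:

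| Weight at entry | Loss to reach 15 kg | Share of body weight |
|---|---|---|
| 20 kg | 5 kg | 25% |
| 25 kg | 10 kg | 40% |
| 30 kg | 15 kg | 50% |
| 35 kg | 20 kg | 57% |

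A child must lose more than this to be flagged. Only children entering close to 15 kg could be flagged after a small loss.

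**2. Height and BMI.** With no limits and no row respectively, neither can be classified. Their shift tables carry no information.

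**3. What absolute change shows.** The documents give no growth figure, so I assume a normal height gain of 4-7 cm a year. The span from Day 0 to Week 48 is 336/365.25 = 0.92 years. Expected gain = rate x 0.92. A half-rate child gains half of that and has a deficit of the same size. Change in z = -deficit/SD, with an assumed height SD for age of 5-7 cm:

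| Assumed rate (cm/year) | Normal gain (cm) | Half-rate gain (cm) | Change in z, SD 7 | Change in z, SD 5 |
|---|---|---|---|---|
| 4 | 3.68 | 1.84 | -0.26 | -0.37 |
| 5 | 4.60 | 2.30 | -0.33 | -0.46 |
| 6 | 5.52 | 2.76 | -0.39 | -0.55 |
| 7 | 6.44 | 3.22 | -0.46 | -0.64 |

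On the planned scale the half-rate child shows a gain of 1.8-3.2 cm and no flag. A child who stops growing shows 0 cm, which would stand out. Baseline height is taken at screening, up to 28 days before Day 0. Counting from there multiplies the spans by at most 364/336 = 1.08 and changes nothing of substance.

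**4. Could a group shift be seen?** Assume the SD of change in z is 0.2-0.4. The 95% half-width is t x SD/√n. For n = 30 it is 2.045 x 0.2/5.48 = 0.07 to 2.045 x 0.4/5.48 = 0.15, so a mean shift of -0.26 to -0.64 would be visible. For the minimum stratum of 8 it is 2.365 x 0.2/2.83 = 0.17 to 2.365 x 0.4/2.83 = 0.33, so the smaller shifts might not be.

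**5. Would a z < -2 category do?** To cross -2 after losing 0.26 to 0.64, a child must start between -2 and -1.74 to -1.36. If baseline z is standard normal (assumption), that share is 0.041 - 0.023 = 1.8% to 0.087 - 0.023 = 6.4%, or about 0.5 to 2 of 30 children. The category misses most half-rate growth, whereas change in z does not.

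**6. Age precision.** SAP 4.2.2 derives age at consent in whole years, so it can be almost a year too low. The error in height z is then up to 4/7 = 0.57 to 7/5 = 1.4. A fixed error largely cancels in within-child change, but only if age advances between visits. If consent age were used throughout, normal growth would appear as a rise of 3.68/7 = 0.53 to 6.44/5 = 1.29, and the original problem would return.

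**The case against.** A reader might infer that the study cannot show growth faltering at all, or that these outputs would look reassuring whatever happened. The documents do not support that. Weight loss would appear as a negative minimum change, and arrested height as a change near zero. Both would also be seen in the individual plots and listings. The gap is partial slowing.

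A reader might also infer that growth is a named safety endpoint. Vital signs are, but Protocol 8.2.3 limits them to temperature, pulse and blood pressure, and Protocol 8.2.5.1 places weight and height under other safety assessments. Only the SAP merges them. No objective mentions growth, and the benefit/risk section raises no growth concern.

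There is a further route: Protocol 8.3.7 has new or aggravated clinically relevant examination findings reported as adverse events. It depends on the investigator's judgement. The same section limits reporting of vital-sign deterioration to serious events or those causing discontinuation, so the route is partial.

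The objection to reading z-scores as self-interpreting stands. A change near zero is expected in the reference population. These children have severe asthma, take regular inhaled corticosteroids and may take oral ones. Nothing in the documents shows that their z-scores would otherwise stay flat.

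Finally, the study is descriptive and z-scores could be derived later from the listings. That is true subject to age precision, but planning the derivation now is the way to secure exact age.

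**Conclusion.** The point holds as a limited, inexpensive improvement to a safety output. The classification that the SAP requires is uninformative for weight and empty for height and BMI. The remaining outputs would show weight loss or arrested growth, but would not separate partial slowing from normal growth.

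The table facts need no assumption. The illustrated size, a half-rate child still gaining 1.8-3.2 cm against a change in z of about -0.26 to -0.64, rests on the assumed growth rate and SD. Precision rests on the assumed SD of change. No primary or secondary conclusion is affected. Even with z-scores, a single-arm study of about 30 children could describe a departure from the reference but not attribute it to treatment.

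**What to change.** In SAP 3.3.6.3 and 4.2.14:

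- Derive age- and sex-specific z-scores for height, weight and BMI from a named reference, for example the CDC growth charts that the protocol already cites. Confirm that the chosen reference covers all three measures, since the protocol uses only its weight distribution.
- Use exact age on the date of each measurement where date of birth is available. Say how age is advanced where it is not, and mark those z-score levels as imprecise.
- Make z-score and change in z-score from baseline at Weeks 16, 24 and 48 the main output, with individual values listed.
- Remove the low/normal/high shift tables based on Tables 2 and 3 for these three variables. A z below -2 or above 2 category may be added as a supplement only.
- State the limits: growth is not a named protocol endpoint; background inhaled or oral corticosteroids and an external reference (a US one for Japanese children) restrict attribution; whole-year age makes levels imprecise.

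The cost is SAP wording and one derivation from height and weight already scheduled, plus sex and age. No new visit or measurement is needed.

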4.2.15 ECG variable

The outcome of the overall investigator ECG evaluation recorded as normal or abnormal with any abnormalities recorded as not clinically significant or clinically significant will be listed for all patients by safety analysis set.

Abnormal values will not be recorded as AEs unless deemed clinically significant.

A summary table will be produced for baseline ECG evaluation to display normal, abnormal – not clinically significant, abnormal – clinically significant and not done. ECG data will also be listed by safety analysis set.

A shift table will be produced for each ECG parameter to display normal (includes borderline), abnormal - not clinically significant, abnormal - clinically significant, and not done. The shift tables will present baseline and last observation post-baseline value.

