1 PROTOCOL SUMMARY

1.1 Schedule of Activities (SoA)

Table 1 Schedule of assessments

| | Part A – PK, PD, Safety | | | | | | | | | | Part B- Safety | | | | DXD/ WD | For details see Section |
|---------------------------------|------------------------------------|----------|----------------|----------------|----------------|----------------|----------------|----------------|----------------|------------|------------------|------------------|------------------------|------------------------|------------|----------------------------------|
| | 1 SCRN Days -28 to -14 | 2 | 3 +1 day | 4 ±3 day | 5 ±4 day | 6 ±7 day | 7 ±7 day | 8 ±7 day | 9 ±7 day | 10 | 11 ±7 days | 12 ±7 days | 13 EOT ±7 day | 14 F/U ±7 day | | |
| Visit | | | | | | | | | | | | | | | | |
| Visit windows | | | | | | | | | | | | | | | | |
| Week | - | 0 | 0 | 1 | 2 | 4 | 8 | 12 | 16 | 24 | 32 | 40 | 48 | 52 | - | Section |
| Day | - | 0 | 1 | 7 | 14 | 28 | 56 | 84 | 112 | 168 | 224 | 280 | 336 | 362 | - | - |
| Written informed consent/assent | X | | | | | | | | | | | | | | | Appendix A 3 |
| Inclusion/exclusion criteria | X | X | | | | | | | | | | | | | | 5.1, 5.2 |
| ACQ-IA | X | X | | X | X | X | X | X | X | X | X | X | X | X | | 8.1.2 |
| PGIC-IA | | | | | | | | | X | X | X | | X | | | 8.1.2 |
| CGIC | | | | | | | | | X | X | X | | X | | | 8.1.2 |
| Body weight and height | X | | | | | | | | X | X | | | X | | | 8.2.5.1 |
| Patient stratification | X | | | | | | | | | | | | | | | 6.1 |
| Vital signs | X | X | X | X | X | X | X | X | X | X | X | X | X | X | | 8.2.3 |
| Medical/surgical history | X | X | | | | | | | | | | | | | | 8.2.5.2 |
| 12-lead ECG | X | | | | | | | | X | | | | X | | | 8.2.4 |

Table 1 Schedule of assessments

| | Part A – PK, PD, Safety | | | | | | | | | | Part B- Safety | | | | | DXD/ WD | For details see Section |
|--|------------------------------------|----------------|-----------|-----------|-----------|----------------|----------------|-----------|----------------|----------------|----------------|----------------|-------------------------|------------------------|---|-----------------|----------------------------------|
| | 1 SCRN Days -28 to -14 | 2 | 3 | 4 | 5 | 6 | 7 | 8 | 9 | 10 | 11 | 12 | 13 EOT ±7 days | 14 F/U ±7 day | | | |
| Visit | | | | | | | | | | | | | | | | | |
| Visit windows | | | +1 day | ±3 day | ±4 day | ±7 day | ±7 day | ±7 day | ±7 day | ±7 day | ±7 days | ±7 days | ±7 day | ±7 day | | | |

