8.2.4 Electrocardiograms

A 12-lead ECG will be obtained as outlined in [Table 1](#) using the site's own ECG machines after the patient has rested in the supine position for at least 10 minutes.

The investigator or authorised delegate will judge the overall ECG as normal or abnormal and report this evaluation. If abnormal, it will be further documented as to whether the abnormality is clinically significant by the Principal Investigator. For all abnormalities (regardless of clinical significance), the specific type and nature of the abnormality will be documented. Clinically significant findings should also be documented on the AE page of the eCRF if applicable.

The investigator or authorised delegate may add extra 12-lead resting ECG safety assessments if there are any abnormal findings or if the investigator considers it is required for any other safety reason. These assessments should be entered as an unscheduled assessment.

All ECG readings will be digitally stored as source documents. Additionally, ECG readings can be printed and placed in the subject's source file.

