3.3.6 Safety outcome variables

The following safety data will be collected: reported AEs (including SAEs), haematology, clinical chemistry, urinalysis, 12-lead electrocardiogram (ECG), physical examination and vital signs.

All safety measurements will use all available data for analyses, including data from unscheduled visits and repeated measurements.

Change from baseline to each post-treatment time point where scheduled assessments were made will be calculated for relevant measurements. AEs will be summarised by means of descriptive statistics and qualitative summaries.

No safety data will be imputed. The handling of partial/missing dates for AEs is detailed in [Appendix I](#).

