3.3.6.4 ECG

A 12-lead ECG will be obtained as outlined in Table 1 of the CSP using the site's own ECG machines after the patient has rested in the supine position for at least 10 minutes.

The outcome of the investigator's overall ECG evaluation will be recorded as normal/abnormal in the CRF and with any abnormalities recorded as not clinically significant or clinically significant. Changes from baseline in continuous 12-lead ECG variables will be calculated at relevant visits as specified in [Table 1](#).

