4.2.13 Laboratory variables

All continuous laboratory parameters will be summarized descriptively by absolute value by each planned visit by treatment/weight group, together with the corresponding changes from baseline using the safety analysis set. These summaries will be produced for the on-study period, as defined in section 3.1.3. The summary statistics presented will be the minimum, 1st quartile, median, 3rd quartile, maximum, mean and SD. Mean changes from baseline over time will also be plotted by treatment group. All variables will be summarized in SI units, with the exception of blood eosinophil counts which will be summarized in both SI and conventional units.

Central laboratory normal reference ranges will be used for the identification of abnormalities. A shift table will be produced for each laboratory variable to display low, normal, high and missing values. The shift tables will present baseline and maximum/minimum/last post-baseline values for each variable.

Shift plots showing each individual patients' laboratory value at baseline and at maximum/minimum/last value post-baseline will be produced for each continuous laboratory variable. If any laboratory variables show any unusual features (high or low values or a general shift in the data points) at other time points then shift plots of these data may be produced. The diagonal line of no change, and horizontal and vertical reference lines indicating the limits of the normal reference ranges, will also be displayed on the shift plots.

Maximum post-baseline TBL elevations by maximum post-baseline ALT and AST will be presented, expressed as multiples of ULN. TBL will be presented in multiples of the following ULN ≤ 1.5 , >1.5 -2, >2 , and AST and ALT will be presented in multiples of the following ULN ≤ 1 , >1 -3, >3 -5, >5 -10, >10 .

Maximum post-baseline TBL will be presented (<2 and ≥ 2 x ULN) against maximum post-baseline ALT (<3 , ≥ 3 - <5 , ≥ 5 - <10 , and ≥ 10 x ULN), expressed as multiples of ULN. This will be repeated to show maximum post-baseline TBL against maximum post-baseline AST. Data for patients with ALT or AST ≥ 3 x ULN, and bilirubin ≥ 2 x ULN will be presented, which will include all visits for this subset of patients.

For urinalysis data, a shift table will be generated to present changes from baseline to maximum post-baseline value for each variable and will include subjects with both baseline and post-baseline data.

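### The ECG shift table takes only the last post-baseline ECG, so an abnormality that has resolved by then is tabulated as normal (minor)

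*SAP*

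**What the plan says.** SAP 4.2.15 plans three ECG outputs: a listing of all evaluations, a summary table at baseline only, and a shift table. The shift table's categories are given as: "A shift table will be produced for each ECG parameter to display normal (includes borderline), abnormal - not clinically significant, abnormal - clinically significant, and not done". Its time points are given as: "The shift tables will present baseline and last observation post-baseline value". No by-visit table and no worst-value table is planned.

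Protocol Table 1 schedules the 12-lead ECG at screening, Visit 9 (Week 16) and Visit 13 (Week 48). Protocol 8.2.4 adds that the investigator "may add extra 12-lead resting ECG safety assessments if there are any abnormal findings", or for any other safety reason. On recording them it says: "These assessments should be entered as an unscheduled assessment".

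For safety data in general, SAP 3.3.6 states: "All safety measurements will use all available data for analyses, including data from unscheduled visits and repeated measurements". For laboratory variables SAP 4.2.13 states: "The shift tables will present baseline and maximum/minimum/last post-baseline values for each variable". SAP 4.2.14 has the same rule for vital signs. The urinalysis shift tables, which are categorical like the ECG table, take the maximum after baseline (SAP 4.2.13).

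SAP 3.3.6.4 also promises a quantitative analysis: "Changes from baseline in continuous 12-lead ECG variables will be calculated at relevant visits".

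**The concern.** A shift table is meant to show at a glance whether anyone got worse on treatment. One built on the last value answers a different question, namely where patients ended up. A child with an abnormal ECG at Week 16, or on an unscheduled recording, whose Week 48 ECG is normal enters the normal column. If baseline was also normal, the child counts as unchanged.

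The effect runs in one direction. Extra ECGs may be taken because something looked abnormal, and SAP 3.1.4 lets an unscheduled value serve as the last value. A later normal repeat can therefore displace the abnormal ECG that prompted it, whereas the table has no route by which a resolved abnormality is counted. At stake is how faithfully one safety table in a long-term safety study reflects the recordings made. No PK, PD or efficacy result depends on it.

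**Working it through.** The plan gives no figure here to reproduce. The check sets the tabulation rule against the ECG schedule.

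**Inputs.** Scheduled post-baseline ECGs: Week 16 and Week 48 (Protocol Table 1). Post-baseline value used: the last one (SAP 4.2.15). Ordered categories: normal (N), abnormal not clinically significant (NCS), abnormal clinically significant (CS). Planned patients: 30 aged 6 to 11 years, plus up to 3 Japanese patients aged 12 to 14 (Protocol 9.2).

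**Step 1: ECGs that can enter the table.** A patient with both scheduled ECGs contributes 2 recordings, of which the table uses 1.
- 30 completers: 30 × 2 = 60 scheduled ECGs, 30 used.
- 33 completers: 33 × 2 = 66 scheduled ECGs, 33 used.

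Every unscheduled ECG that is not the last one also drops out. The documents give no expected number of these, and it may be zero.

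**Step 2: patterns where last and worst differ.** Two visits with three categories give 3 × 3 = 9 patterns. Last is milder than worst in three of them:

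| Week 16, Week 48 | Worst | Last | Table shows, baseline N | Table shows, baseline NCS |
|---|---|---|---|---|
| NCS, N | NCS | N | no change; worsening hidden | improved; no worsening occurred |
| CS, N | CS | N | no change; worsening hidden | improved; worsening hidden |
| CS, NCS | CS | NCS | shift to NCS; understated | no change; worsening hidden |

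From a normal baseline, 2 of 9 patterns are a worsening shown as normal to normal, and 1 more is understated. From an NCS baseline, 1 of 9 is a worsening shown as no change and 1 is a worsening shown as improvement. From a CS baseline no worsening is possible. These are counts of patterns, not probabilities.

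**Step 3: where a missed finding can still be seen.**
- NCS: SAP 4.2.15 keeps abnormal values out of the adverse events unless they are clinically significant, so a transient NCS finding is in the listing and in no summary.
- CS: Protocol 8.2.4 sends it to the adverse event page if applicable, and SAP 4.2.12.1 then tabulates it by system organ class, preferred term, causality and maximum intensity. The shift table could still show normal to normal for the same patient, so two outputs would appear to disagree.

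**Step 4: scale, under an assumption.** The documents give no rate of transient abnormalities. If each of 30 patients independently had probability p of one that resolves before the last ECG, the chance of at least one is 1 − (1 − p)^30: 45.5% at p = 2%, 78.5% at 5% and 95.8% at 10%. The rates are assumed, do not separate NCS from CS, and carry no weight in the severity below.

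**Step 5: continuous variables.** SAP 3.3.6.4 promises changes from baseline at visits given in Table 1. SAP 4.2.15 plans no summary of such changes, SAP Table 1 has no ECG column, and neither SAP section names an ECG interval.

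**The case against.** The strongest reply is that little is hidden. There are some 30 to 33 patients with two scheduled post-baseline ECGs each, and a full listing, so every transient abnormality can be read directly. ECG is not among the safety endpoints in Protocol Table 2 or SAP 1.1.3. Protocol 9.5.5 asks for shifts to the most extreme value for laboratory variables only, and for ECG asks just that results be documented as normal or abnormal. The SAP already goes further than that. All of this stands, and it sets the severity.

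Two stronger readings are tempting and should not be adopted:
- A reader might infer that a transient clinically significant abnormality would appear only in a listing. The adverse event route in Protocol 8.2.4 and SAP 4.2.15 says otherwise, although its qualifier (if applicable) leaves some latitude.
- A reader might infer that the last-value rule breaches SAP 3.3.6. It need not: SAP 3.1.4 admits unscheduled data to maximum, minimum or last values, and an unscheduled ECG can be the last value.

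It is also fair to say that maximum and minimum come naturally to continuous data, so the laboratory and vital-sign comparison is imperfect. The urinalysis tables answer this: they are categorical and still use the maximum. The SAP gives no reason for treating ECG differently.

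**Conclusion.** The point holds as a minor reporting gap. For a patient with a Week 48 ECG, the only post-baseline ECG table omits the Week 16 ECG and any earlier unscheduled one, which is half of the scheduled post-baseline recordings among completers. An abnormality that has resolved by the last ECG is tabulated as normal. The practical loss is mainly for findings judged not clinically significant.

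Limits: the display is no change only where the baseline category equals the last one; from an abnormal baseline the same patient may appear improved. Where no Week 48 ECG exists, the Week 16 or a later unscheduled ECG is the last observation and is tabulated. The 30 of 60 counts recordings not used, not abnormalities missed.

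The mismatch over continuous ECG variables is a secondary wording matter. One might infer that intervals are not recorded at all, because Protocol 8.2.4 describes only an overall judgement and the nature of any abnormality. The case report form is not part of the documents, so the supportable statement is only that the SAP announces a calculation and plans no output for it.

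**What to change.** In SAP 4.2.15, add a panel of baseline against worst post-baseline evaluation, with the order clinically significant abnormal, then not clinically significant abnormal, then normal. Include unscheduled and repeat ECGs, and keep the last-observation panel beside it. State that not done applies only when a patient has no post-baseline ECG evaluation, and name the period covered. From a normal baseline, the three understated patterns would then show at their worst grade, and all 60 scheduled ECGs of 30 completers would inform the table.

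Reconcile SAP 3.3.6.4 with 4.2.15: either delete the change in continuous variables, or name the intervals recorded and plan a summary of them. Clarify at the same time whether the shift table concerns the overall evaluation or separate parameters.

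The cost is a few lines of SAP text and one programming change for the panel. The evaluations it needs are already collected, and the present table is kept.
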